9.6.4 Left Atrial Size and Function

Left atrial (LA) size will be measured in the anteroposterior (parasternal long-axis), transverse and longitudinal dimensions (apical 4-chamber). LA volumes will be calculated using the biplane area-length method: $(0.85 \times 4\text{-chamber LA area} \times 2\text{-chamber LA area}) / \text{LA length}$. The length is measured from the middle of the plane of the mitral annulus to the superior aspect of the LA (shortest of 4- and 2-chamber measurements). LA volumes will be indexed for body surface area.

Where suitable datasets are obtained, 3D LA volumetric analysis and assessment of LA function and strain will also be performed.

9.6.5 Additional Echocardiography Parameters

The following parameters will be obtained in all participants:

- Tricuspid annular plane systolic excursion (TAPSE) for estimation of right ventricular function using pulse-wave Doppler.
- Where applicable, mitral regurgitation dP/dt.

9.7 Laboratory Evaluations

The use of biomarkers that can affect treatment decisions in AF is at an early stage of development.⁸⁸ The RATE-AF trial will allow us to collect and store blood samples on patients at baseline and follow-up, providing a unique biobank of AF patients receiving rate-control. In collaboration with the Human Biomaterials Resource Centre (HBRC) at the University of Birmingham, we will also isolate DNA for future work on predictors of response, including known polymorphisms of rate-responsiveness.⁸⁹

Laboratories at each clinical site will process the standard laboratory investigations required as part of standard clinical care (see **Section 9.1**). Trial laboratory evaluations will be performed at the core laboratory and processed according to the guidelines in **Sections 9.7.1, 9.7.2 and 9.7.3**.

9.7.1 Laboratory Assays

NT-pro B-type natriuretic peptide will be analysed using a Sandwich immunoassay using monoclonal ruthenium labelled antibody and Roche Cobas 8000 e602. The total coefficient of

variation for repeatability with this assay is <2% with an estimated volume of 250 microlitres required for each test and measurement range of 5-35000 pg/mL (0.6-4130 pmol/L).

9.7.2 Cellular Response to Rate Control

The effect of baseline and follow-up serum on intracellular sodium/calcium, force of contraction and activation of ERK1/2-dependent cascades will be examined in human induced pluripotent stem cell-derived cardiomyocytes, using well-established integrated fluorescence/contractility photometry and western blotting techniques.^{90, 91} DigiFAB⁹², will be used to determine whether changes are dependent on endogenous cardiotoxic steroids, which can modulate intracellular ion concentration in cardiomyocytes^{93, 94}, and potentially contribute to treatment discontinuation (or the development of toxicity).⁹⁵ The concentration of serum cardiotoxic steroids will be determined using liquid chromatography–tandem mass spectrometry. Individual change in cardiotoxic steroids and intracellular sodium/calcium will be correlated with the change in heart rate, LVEF, B-type natriuretic peptide and quality of life. In addition, we will identify patterns in patients withdrawing from treatment or experiencing adverse reactions.

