3.5 Exploratory objectives

- Correlation of baseline measures, including QoL questionnaires and unblinded baseline investigations such as QoL, BNP, LVEF, E/e', EHRA, intracellular methods and heart rate.
- Impact of therapy on intracellular sodium and calcium concentration and cardiotonic steroid levels as biomarkers of cellular response at six and twelve months.
- Impact of combination therapy on outcomes, including comparison of bisoprolol/non-dihydropyridine calcium channel blocker (CCB) vs. bisoprolol/digoxin vs. digoxin/CCB vs. single therapies.
- Change in cognitive function at twelve months

- Qualitative research of patient-reported QoL using focus groups to explore patient acceptability, optimal delivery methods and responsiveness.
- Assessment of the validity and reproducibility of echocardiographic measures in patients with AF.
- Correlation of serum digoxin concentration with change in QoL and intracellular methods.
- Cost-consequence economic analysis from an NHS perspective.

4 Selection of Participants

Participants who potentially fulfil the inclusion criteria for this trial must have their eligibility confirmed by medically qualified personnel with access to and a full understanding of the potential participant's medical history. If eligibility has been assessed and documented by medically qualified personnel, then the process of obtaining informed consent may be delegated as appropriate and as documented on the **RATE-AF** Delegation and Signature Log.

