7.1 Treatment

The Investigational Medicinal Products (IMPs) for this trial are Digoxin and Bisoprolol.

At randomisation, participants will be allocated to open-label treatment with either Digoxin 62.5 – 250 µg od or Bisoprolol 1.25 – 15 mg od.

Digoxin

Digoxin is a cardiac glycoside derived from the foxglove plant. The cardiac effects of digoxin therapy are summarised by:

- Positive inotropic effects: increased intracellular calcium due to direct inhibition of sodium-potassium adenosine triphosphatase (Na/K-ATPase)
- Negative chronotropic effects: decreased conduction velocity through the atrioventricular node, an increase in the effective refractory period and an increase in vagal activity leading to sinus node depression.

Clinically, digoxin is commonly prescribed in two conditions, heart failure and AF.

Bisoprolol

Bisoprolol fumarate is a highly beta-1 selective adrenoreceptor blocker first approved by the U.S. Food and Drug Administration in 1992. The cardiac effects of bisoprolol therapy are summarised by:

- Negative chronotropic effects: a reduction in resting and exercise heart rate due to prevention of norepinephrine and epinephrine from binding to the beta-receptor in cardiac conduction tissue.
- Negative (mild) inotropic effects: an initial fall in resting and exercise cardiac output with little observed change in stroke volume and only a small increase in right atrial pressure or pulmonary capillary wedge pressure.

Clinically, bisoprolol is commonly prescribed in a range of cardiology conditions, including post-myocardial infarction, heart failure and in patients with atrial tachyarrhythmia, including AF.

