7.4 Drug Interactions and Contraindications

Digoxin

Following oral administration of digoxin, approximately 60–85% of the dose is usually absorbed, mainly from the small intestine. The onset of action is 0.5-2 hours and maximal effects occur in 2-

6 hours. Digoxin has a large volume of distribution and approximately 20-30% of digoxin in blood is bound to plasma proteins. Metabolism is minimal but variable, with the majority of drug excreted unchanged in the urine by glomerular filtration and tubular secretion. With normal renal function, the elimination half-life is 34-44 hours which is prolonged in patients with renal failure by two to threefold. Dose adjustment is unnecessary in patients with hepatic impairment. Therapeutic plasma concentrations of digoxin have been described as 0.5-2.0 ng/mL.⁷⁰ In digoxin-naïve patients with normal renal function, approximately seven days are required to reach steady-state therapeutic concentrations if a loading dose is omitted. As such, the majority of clinicians prescribe one or two loading doses, totalling 500 to 1000 µg over 24 hours.

Caution is recommended in patients with electrolyte disturbance (due to increased risk of toxicity) and reduced doses are recommended in patients with renal impairment. There are no concerns in pregnancy or with breast-feeding, although dose adjustment may be required.

Contraindications for digoxin therapy include heart block, accessory pathway supraventricular tachycardia and a current diagnosis of obstructive hypertrophic cardiomyopathy, myocarditis or constrictive pericarditis.

Digoxin has been associated with a number of adverse effects, although data from randomised trials show little difference in comparison to placebo, apart from cases of toxicity (2% versus 0.9% respectively in the DIG trial of patients with HF)⁷¹. The most common side effects are gastrointestinal upset, dizziness, blurred vision, headache and rash. In toxic states (serum levels >2 ng/mL), digoxin is pro-arrhythmic and can aggravate heart failure, particularly with co-existent hypokalaemia. In cases of overdose, repeated early doses of activated charcoal may be given to reduce absorption and in severe toxicity, digoxin-specific antibody fragments are available as an intravenous infusion.

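### The exploratory cellular-marker correlations in Protocol 9.7.2 are not conditioned on arm or digoxin exposure, so a drug effect on both sides could pass for an individual-level link

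*Protocol*

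**What the plan says.** Under Protocol 9.7.2, participants' baseline and follow-up serum is applied to stem-cell-derived cardiomyocytes, intracellular sodium and calcium are read, and serum steroid concentrations are measured. The stated analysis is: "Individual change in cardiotoxic steroids and intracellular sodium/calcium will be correlated with the change in heart rate, LVEF", B-type natriuretic peptide and quality of life. The section then adds that "we will identify patterns in patients withdrawing from treatment or experiencing adverse reactions".

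The matching objective in Protocol 3.5 is "Impact of therapy on intracellular sodium and calcium concentration and cardiotonic steroid levels as biomarkers of cellular response at six and twelve months". It names no method. SAP 9.7 offers only simple summaries by group for data outside the pre-specified outcomes. The optional sub-studies in Protocol 9.9 and 9.10 each promise an analysis plan before data access; 9.7.2 does not.

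On mechanism, Protocol 7.1 lists for digoxin "increased intracellular calcium due to direct inhibition of sodium-potassium adenosine triphosphatase". On exposure, Protocol 7.6 keeps patients in the trial if they start the other arm's drug and expects therapy to be added. On sampling, Table 1 schedules the stored sample at baseline and month 6 only.

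**The concern.** Follow-up serum from a patient taking digoxin contains a drug that acts on the measured pathway, so the marker change can differ between arms whatever the patient's own biology. The trial also tests whether the arms differ in quality of life, LVEF, BNP and heart rate. If both differences exist, the two arms form two separated clouds of points. A correlation through both clouds reflects the gap between them, even with no relation inside either. It would restate the randomised comparison while appearing to show that a patient's marker change tracks that patient's response.

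The search for patterns in patients who stop has a related weakness. Section 9.7.2 suggests that these steroids may contribute to discontinuation. For some patients, however, the follow-up marker will reflect the fact that they had stopped, which reverses the direction of inference.

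**Working it through.** **The plan's own figure.** Section 9.7.2 gives no sample size, so the trial's is used (Protocol 12.2: two-sided alpha 0.05, power 85%, effect 0.5 SD). Per arm, n = 2(1.960 + 1.036)² / 0.5² = 71.8, so 72, or 144 in total. Allowing for 10% loss, 144 / 0.9 = 160. Both figures reproduce.

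**Pooled correlation with no individual-level link.** Let dx and dy be the arm differences in marker change and clinical change, in within-arm SDs. With 1:1 allocation and zero within-arm correlation:

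r = (dx·dy/4) / √[(1 + dx²/4)(1 + dy²/4)]

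- dx = 1, dy = 0.5: 0.125 / √(1.25 × 1.0625) = 0.108
- dx = 2, dy = 0.5: 0.25 / √(2 × 1.0625) = 0.171

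At n = 144 the two-sided 5% critical value is |r| = 0.164. The documents give no value for dx. They give dy = 0.5 only as the design effect for quality of life.

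**Share of simulated trials with p<0.05** (n = 144, no within-arm link):

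| dx | dy | pooled | conditioned on arm |
|---|---|---|---|
| 1 | 0.5 | 25% | 5% |
| 1.5 | 0.5 | 42% | 5% |
| 2 | 0.5 | 54% | 5% |
| 1 | 0.2 | 8% | 5% |
| 2 | 0.2 | 13% | 5% |
| 1 or 2 | 0 | 5% | 5% |

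With 100 evaluable patients the dy = 0.5 rates are about 20% to 40%.

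**Is an arm term enough?** Arm is not the same as exposure, because Protocol 7.6 allows the other arm's drug. Take dx = 2 and dy = 0.5, let both shifts follow actual digoxin exposure, and assume that a share of each arm has the opposite exposure. The arm-adjusted test then rejects in about 15% of trials when that share is 10%, and in about 31% when it is 20%. Adding a term for actual exposure returns the rate to about 5%.

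**Patients who stop.** Protocol 7.4 states: "With normal renal function, the elimination half-life is 34-44 hours", and two to three times longer in renal failure (68 to 132 hours). Taking five half-lives as washout (an assumption; 0.5⁵ = 3% remaining):

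- 5 × 34/24 = 7.1 days to 5 × 44/24 = 9.2 days
- prolonged: 5 × 68/24 = 14.2 days to 5 × 132/24 = 27.5 days

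A patient who stopped digoxin about one to four weeks or more before the month 6 sample, and who still gives blood, therefore provides off-drug serum.

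**The case against.** The strongest reply is that the text is silent and does not commit to pooling. A reader might infer a decision to ignore arm, but one sentence in a laboratory section does not show that. This stands: the defect is an omission, although a literal reading permits the pooled test.

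The size is also open to challenge. The marker shift has no source in the documents, and 0.5 SD is stated only for quality of life. Bisoprolol acts on heart rate too, through "a reduction in resting and exercise heart rate due to prevention of norepinephrine and epinephrine from binding to the beta-receptor", so the arms may differ little on that pairing. With no clinical difference there is no artefact. All of this stands.

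Some planned work bears on the point. Protocol 3.5 lists a correlation of serum digoxin concentration with change in quality of life and with the intracellular methods. That is an exposure analysis, but it leaves the 9.7.2 correlation unconditioned. The DigiFAB step is meant to test dependence on endogenous steroids. However, Protocol 7.4 describes digoxin-specific antibody fragments as a treatment for digoxin toxicity, so reversal alone would not clearly separate trial digoxin from endogenous steroid.

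A reader might also infer that patients who stop are, in general, sampled after washout. The documents do not support this. Those who stop after month 6 already have an on-drug month 6 sample. Those followed only by mailed questionnaires (Protocol 8.7) may have no follow-up sample.

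Finally, no primary, secondary or feasibility result depends on this analysis, and Protocol 12.1.3 requires exploratory analyses to be labelled as such.

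**Conclusion.** The point holds as a gap in specification. Neither document conditions these correlations on arm or digoxin exposure, and digoxin acts directly on the marker side. Pooling could therefore produce r of about 0.11 to 0.17, declared significant in about 25% to 55% of trials, with no individual-level link. That range assumes 144 evaluable patients, a marker shift of 1 to 2 SD and a clinical difference of 0.5 SD. It drops to about 8% to 13% at a clinical difference of 0.2 SD and to the nominal 5% at zero. The true size cannot be fixed from the documents.

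The washout issue is narrower. It is an inference from the schedule and half-lives, and it applies only to patients who stop digoxin well before month 6 and still give blood. Baseline serum is unaffected. The matter is minor for the trial's main conclusions, but it bears directly on any mechanistic claim drawn from 9.7.2.

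**What to change.** In Protocol 9.7.2, or in a short analysis plan agreed before data access as for 9.9 and 9.10, state the following.

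1. These exploratory associations will be estimated by regressing each clinical change on marker change, with terms for randomised arm and for actual digoxin exposure at sampling. Within-arm correlations will also be shown. Exposure comes from the medication record and serum digoxin, both already collected. Protocol 7.7 describes the serum level for the digoxin arm, so in the bisoprolol arm the medication record may have to serve.
2. For withdrawal and adverse reactions, the baseline serum marker is the main predictor. Follow-up marker values are reported by on- or off-drug status at sampling. Patients who have stopped should stay in this description: limiting it to those still on the allocated drug would select on a post-randomisation variable and remove the group of interest.

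In the same edit, reconcile the six- and twelve-month cellular objective in 3.5 with the stored-sample row of Table 1, which stops at month 6. Also say how a month 6 marker change is to be paired with an LVEF change measured to month 12.

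The cost is one or two degrees of freedom and slightly less power for a true association. The adjusted estimate also answers a narrower question: whether the marker carries information beyond arm and digoxin exposure. No new samples or assays are needed.

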9.7.3 Stored Blood Samples

Blood samples will be stored at HBRC for future biomarker and genetic analysis, with participants providing explicit consent for this process. Any future use of these samples will be undertaken with ethical approval.

9.7.4 Specimen Preparation, Handling, Storage and Shipment

Specimens will be handled according to local standard operating procedures consisting of the time requirements for processing, required temperatures, aliquots of specimens, where they will be stored, how they will be labelled, the process for remnant samples/disposal and appropriate instructions for transportation.

9.8 Economic Evaluation

The RATE-AF trial will allow determination of the most appropriate data collection methods and ease of acquiring resource use and cost data for a subsequent outcomes trial. Specifically, how data is obtained from secondary care records, patient-reported resource use and the feasibility of obtaining primary care records. A preliminary economic evaluation from an NHS perspective will be performed to estimate costs over the 12-month period. The patient-level cost-analysis will determine all AF-related costs, with respect to trial interventions and secondary-care resource use (including adverse events) in the two arms of the trial. We will collect both cost and outcome data and present them in a cost-consequence analysis. Costing for this trial suggests that simplifying medication alone could result in a saving of £5900 over each 12-month period. Considering the high and increasing prevalence of AF, this could result in a substantial NHS cost savings, particularly if adverse reactions are also reduced. The aim of this objective within the trial is to

prepare the groundwork for a future cost-per-quality adjusted life year (QALY) analysis of rate-control in AF.

Costs of care will be derived from patient level resource-use data, focusing on secondary care costs, and including adverse effects, such as pacemaker implantation. Other major drivers of cost are hospitalisation (including visits to Accident & Emergency), unplanned outpatient visits and outpatient tests such as echocardiography or ambulatory ECG. The cost analysis will also consider therapy costs, both trial drug and additional treatments. Unit costs will be obtained from standard sources including NHS Reference Costs, Unit Costs of Health and Social Care⁹⁶ and health care providers. Total per-patient health care costs will initially be calculated thus allowing the estimation of mean costs per trial arm over 12 months follow-up. Responses to the EQ-5D-5L questionnaire at baseline, visit 2 (6 months) and visit 3 (12 months) will be used to plan a future QALY analysis.

Key feasibility elements are:

- Determining the best methods for obtaining hospitalisation data, including where participants have been hospitalised outside of research site
- Whether robust primary care costs can be estimated and the method(s) for acquiring this type of data
- How key cost drivers can be incorporated into data collection for any future trial

9.9 Heart rate and physical activity monitoring

Secondary objectives of the RATE-AF trial include assessment of heart rate and physical functioning. Conventional measures of obtaining this information include periodic measurement of pulse rate; apex beat rate and ECG data, and 6-minute walk tests and activity questionnaires respectively. These type of measures are limited to specific time points, and are unable to explore the interaction of heart rate with physical activity in the patients' normal environment. To obtain more detailed information, RATE-AF trial participants will be asked to join an optional sub-study which uses a wearable device connected to a smartphone for a period of 6-12 months. Potential participants will be given a specific Patient Information Leaflet written by the RATE-AF Patient and Public Involvement Team, and asked to sign the RATE-AF optional consent form. Our intention is to enrol 75-100 participants to this sub-study, either at baseline or follow-up visits. The technology for this research is supported by funding from an Innovative Medicines Initiative European Union Horizon 2020 grant (BigData@Heart; <https://www.bigdata-heart.eu/>).⁹⁷ The work will be a collaboration between the University of Birmingham, University College London and Utrecht Medical Centre (the Netherlands), in addition to the Hyve (an IT support company based in the Netherlands), who are all major partners in this initiative.

Wearable device:

A commercially-available wrist-worn device will be used that measures physical activity (movement, activity, physical exercise and step count) and sleep (sleep efficiency, latency, wake

episodes and fragmentation) using heart rate and accelerometer sensors. The device is non-invasive, painless, and extremely low risk. They are similar in size and dimension to a watch, manufactured primarily in rubber, and are marked as lifestyle devices, therefore not denoting participation in a research study, reducing stigmatisation and eliminating the possibility of identifying an individual as a research participant.

Smartphone and software:

Participants will be provided with a suitable Android platform smartphone, which functions as a regular mobile phone and allows users to make calls to all UK landlines and mobiles, or access the internet. Software on the phone will connect with the wearable device and also passively collect information about the environment and phone usage, using sensors which are built into all modern smartphones. This includes the amount of noise and light in surroundings, Bluetooth interactions, local weather conditions, location, length and duration of texts and phone calls, keystrokes, and battery life. GPS location will be anonymised in a way that does not reveal actual geographic location. Similarly, we will not be able to see the content of text messages, or phone numbers that have been contacted. Applications will be installed to record the pulse, AF symptoms and quality of life, and provide an educational resource for patients.⁹⁸

Data handling:

All of the information collected will be pseudo-anonymised and kept confidential. Data collected via the wrist-worn wearable device and smartphone will be encrypted, uploaded to a secure server and will not be identifiable by patient name. Data will be temporarily cached on the smartphone until an appropriate Wi-Fi or mobile data connection is available, and will then be automatically deleted from the phone memory. A contract between the University of Birmingham and The Hyve who will assist with the hosting of the RADAR platform has been made. Data are securely stored in the established RADAR platform (Remote Assessment of Disease and Relapse; <https://www.radar-cns.org/>) . Data collected from the devices will then be processed at the University of Birmingham. The pseudo-anonymised data acquired may be shared with members of the BigData@Heart consortium in the UK and other countries of the European Union, after agreement from the RATE-AF Trial Steering Committee.

Participant support:

Contact will be made with participants by the BigData@Heart team throughout the course of follow-up if there is a loss of data stream from a device. The participant will be contacted by telephone to ensure compliance and correct use. In addition to a telephone call provided after an introductory training session, participants will receive further call as needed to address any concerns or questions, and brief follow-up phone-calls will then be offered as needed to maintain engagement with participants and address any technical concerns.

Objectives and analysis:

The objectives of this sub-study are exploratory – our hypothesis is that periodic ambulatory heart rate and physical activity monitoring will demonstrate a higher correlation with changes in SF36 physical functioning, cardiac function and NTpro-BNP than conventional ECG-derived heart rate, IPAQ score or 6-minute walk distance.⁹⁹ An analysis plan for this sub-study will be agreed before access to data.

Pseudo-anonymised data will also contribute to the BigData@Heart Consortium, which in combination with other studies and registries across the European Union aims to redefine clinical phenotypes of common cardiovascular diseases. Collaboration with the RATE-AF trial will allow development of the remote monitoring platform for capturing patient-related outcomes in this patient group. We will demonstrate the feasibility of the platform for running further studies in the BigData@Heart Consortium, designed to have future impact on improving treatment outcomes in patients with AF.

